6.9.3. Management of gastrointestinal disorders

Early recognition and management of potential GI disorders may mitigate more severe and subsequent toxicities.

6.9.4. Embryo-fetal Toxicity

The effect of ARD-101 on embryo-fetal development has not been tested. Thus, a highly effective form of contraception must be used, and enrolled subjects should receive instructions regarding this during the entire study from enrollment to 90 days after last dose administration.

6.10. Permitted Medications/Procedures

Any medicinal product, prescribed or OTC, including vitamins, natural, and herbal remedies, taken by a subject other than the study medication, is considered concomitant medication.

Any concomitant treatment will be given only if deemed strictly necessary by the Principal Investigator or designee. Use of concomitant medication will be recorded and reported. Particularly, as described in [Section 2.3.2](#), ARD-101 is a substrate of the MDR1, MATE1, MATE2-K, OAT3 and OCT2 transporters. Coadministration of these transporter inhibitors have the potential to alter the pharmacokinetics of ARD-101. Therefore, before placing a subject on a specific medication/therapy, it is the responsibility of the investigator to check on potential drug-drug interactions between that medication/therapy and ARD-101 based on the Drug Development and Drug Interactions: Table of Substrates, Inhibitors and Inducers (<https://www.fda.gov/drugs/drug-interactions-labeling/drug-development-and-drug-interactions-table-substrates-inhibitors-and-inducers>), and Drug-Drug Interaction Database (<https://www.fda.gov/drugs/drug-interactions-labeling/databases>) of FDA.

6.10.1. Permitted Medications/Procedures

Subjects are permitted to use medications consistent with those permitted, including the use of contraceptive medications and hydrocortisone cream. All concomitant medications are subject to approval by the principal investigator.

No concomitant use of approved obesity drugs or diabetes treatment (excluding metformin), MDR1, MATE1, MATE2-K, OAT3, or OCT2 inhibitors, or any drug deemed incompatible with trial participation as per investigator judgement.

7. DISCONTINUATION

7.1. Subject Withdrawal and Replacement

Subject participation may be terminated prior to completing the study and the reason recorded as follows:

1. Adverse event
2. Protocol violation
3. Lost to follow-up
4. Subject withdrew consent at own request
5. Other

A genuine effort must be made to determine the reason(s) why a subject fails to return for the necessary visits or is discontinued from the study. If the subject is unreachable by telephone, a registered letter, at the minimum, should be sent to the subject requesting him/her to contact the clinic.

Withdrawn subjects may be replaced until the full cohort has completed the study.

8. STUDY ASSESSMENTS AND PROCEDURES

For timing of assessments, refer to the Schedule of Assessments [Table 1](#).

8.1. Eligibility Screening

All subjects must sign an informed consent form (ICF) prior to the conduct of any screening procedures. Screening assessments will occur within 28 days prior to the first dose of study medication. The subject's relevant medical history and demographic data will be obtained. Retesting of abnormal screening values that lead to exclusion are allowed during the Screening Period (to reassess eligibility). The last result obtained prior to the first dose of study medication will be used to determine eligibility.

8.2. Safety Variables

8.2.1. Adverse Events

Adverse event reporting will begin for each subject from the date the ICF is signed and will continue until the EOS Visit.

8.2.1.1. Definitions

8.2.1.1.1. Definition of Adverse Event

Any untoward medical occurrence in a patient or clinical investigation subject administered a pharmaceutical product and which does not necessarily have a causal relationship with this treatment. An AE can therefore be any unfavorable and unintended sign (including an abnormal laboratory finding), symptom, or disease temporally associated with the use of a medicinal (investigational) product, whether or not related to the medicinal (investigational) product.

Other untoward events occurring in the framework of a clinical study will be recorded as AEs, e.g. those occurring during treatment-free periods (including screening or post-treatment follow-up periods), in association with study-related procedures and assessments, or under placebo. For study medication, lack of efficacy may be an expected potential outcome and should not be reported as an AE unless the event is unusual in some way, e.g., greater in severity.

Concomitant illnesses, which existed prior to entry into the clinical study, will not be considered AEs unless they worsen during the Treatment Period. Pre-existing conditions will be recorded as part of the subject's medical history.

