	
 ▪ Circulating levels of bile acids, ferritin, leptin, and adiponectin at run-in visit and end of treatment (day 28) performed during the MMTT • Body composition as measured by bioelectrical impedance scale • Body composition and hepatic steatosis by magnetic resonance imaging-derived proton density fat fraction (MRI-PDFF) + full body composition scan pretreatment and end of treatment • The change in homeostatic model assessment for insulin resistance (HOMA-IR) at the end of treatment from the baseline • The change in fasting blood glucose at the end of treatment from the baseline • Hunger and control of eating as measured by Likert and visual analogue scales, respectively • Change in indirect calorimetry • The fecal samples will be collected during the run-in visit and on day 28 for microbiome analysis to evaluate potential effects of the study medication on fecal microbiome profile (optional for subjects) • Phenotypic bitter taste test (using commercially available test strips/kis) during the run-in visit of the study (optional for subjects)
Study Design	
This is a Phase 2, open label study of ARD-101 in subjects with relevant weight regain at least one year after bariatric surgery comparing inpatient metabolic dynamics.
 
A total of approximately 30 subjects (15 post sleeve gastrectomy and 15 post gastric bypass surgery) will be enrolled in the clinical study.
 
A screening process will be initiated upon completion of the informed consent process. Subjects will be assessed for eligibility through screening tests conducted within 28 days prior to enrollment. Following completion of screening tests and confirmation of eligibility, subjects will be enrolled to receive ARD-101.
 
All available safety and tolerability data will be evaluated throughout study conduct. Pharmacodynamic data will be analyzed after study completion.
 
Subjects will be receiving treatment in an outpatient setting and will be instructed to visit the clinical center periodically as scheduled in Table 1 for safety and efficacy assessments. The treatment may be discontinued due to intolerable toxicity, withdrawal of informed consent, discretion of principal investigator or end of the study.
 
All subjects will be followed up for approximately 14 days after the last dose of study drug.

Test Product, Dose, and Mode of Administration	ARD-101 at 200 mg BID administered orally for 28 days

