	
2 years prior to enrollment (Note: one unit = 12 ounces of beer, 4 ounces of wine or 1 ounce of spirits)
 
 16. Smoking any amount within 3 months prior to enrollment 17. Excessive consumption of tea, coffee, and/or caffeinated beverages (more than 8 cups, 250 mL for each cup) every day within 3 months prior to enrollment 18. Symptomatic viral, bacterial (including upper respiratory infection), or fungal (non-cutaneous) infection within 1 week prior to enrollment 19. History of human immunodeficiency virus antibody, hepatitis C antibody or hepatitis B virus surface antigen 20. A history of psychiatric and psychological condition that, in the judgment of the investigator, may interfere with the planned treatment and follow-up, affect subject compliance or place the subject at high risk from treatment-related complications 21. Poor venous access or inability to tolerate venipuncture 22. Any condition or active drug treatment that the investigator or primary physician believes may not be appropriate for participating in the study
Duration of Study	
The duration of participation for each subject will be approximately 84 days (12 weeks)
 
 • Screening Period: Up to 28 days (4 weeks) • Run-in Visit: Up to 14 days (2 weeks) • Treatment Period: 28 days on ARD-101 (4 weeks) • Follow-up Period: 14 days (2 weeks). The End of Study (EOS) Visit will occur within 14 days after receiving the dose of ARD-101
Pharmacodynamic Evaluation	
All subjects will be required to provide blood samples at defined time points and at the end of treatment visit. These blood samples will be used to explore the parameters described in the endpoint setting. The Control of Eating Questionnaire (CoEQ) will be administered at the timepoints indicated in Table 1.

Safety Evaluations	
Adverse events (AE) will be collected from the time of informed consent until 14 days after the last administration of study drug. Safety laboratory assessments, including CBC, chemistries, coagulation tests, urinalysis, and thyroid function, along with ECGs, , and vital signs will be obtained. All concomitant medications will be recorded. All adverse events will be followed to resolution or stabilization. Only TEAE will be summarized.

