4.5. Early Termination

If a subject withdraws prematurely after dosing, all data normally collected should be collected at the time of premature discontinuation. If deemed necessary by the Principal Investigator, the subject will be asked to return at the regularly scheduled EOS Visit.

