8.2.1.2. Recording of Adverse Events

Adverse events should be collected and recorded for each subject from the date the ICF is signed until the end of their participation in the study, i.e., the subject has discontinued or completed the study.

Adverse events may be volunteered spontaneously by the subject, or discovered by study staff during physical examinations or by asking an open, non-leading question such as ‘How have you been feeling since you were last asked?’ All AEs and any required remedial action will be recorded. The nature of AE, date (and time, if known) of AE onset, date (and time, if known) of AE outcome to date, severity and action taken of the AE will be documented together with the Principal Investigator’s assessment of the seriousness of the AE and causal relationship to study drug and/or study procedure.

All AEs should be recorded individually in the subject’s own words (verbatim) unless, in the opinion of the Principal Investigator, the AEs constitute components of a recognized condition, disease or syndrome. In the latter case, the condition, disease or syndrome should be named rather than each individual symptom. The AEs will subsequently be coded using the Medical Dictionary for Regulatory Activities (MedDRA). Severity of AEs will be graded using the Toxicity Grading Scale for Healthy Adult and Adolescent Volunteers Enrolled in Preventive Vaccine Clinical Trials (September, 2007).

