9.7.1. Adverse Events

All AEs will be listed. The number and percent of subjects experiencing an event will be tabulated for each SOC and PT. The AEs will also be tabulated according to intensity and causality. A TEAE is defined as an AE with a start date on or after the first dose of study drug, or that worsened following first administration of study drug. For purposes of data analysis, the end of the TEAE period will be the last time point when a subject was evaluated for AEs.

The AEs (TEAEs) will be tabulated according to intensity and causality, as applicable.

Non-TEAEs will be listed, as applicable.

Serious AEs will be listed separately.

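### The adverse-event rules for pre-existing illness and for subjects who leave early conflict with the protocol's own collection window, so treatment-emergent events may be under-counted

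*Combined protocol and SAP*

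**What the plan says.** On pre-existing illness, section 8.2.1.1.1 states: "Concomitant illnesses, which existed prior to entry into the clinical study, will not be considered AEs unless they worsen during the Treatment Period". Section 4.3 sets the Treatment Period at 28 days on drug and lists Follow-up as a separate period. The preceding paragraph of 8.2.1.1.1 has other untoward events recorded as AEs, including "those occurring during treatment-free periods (including screening or post-treatment follow-up periods". Section 9.7.1 defines a TEAE as an AE that starts on or after first dose "or that worsened following first administration of study drug". It closes the TEAE period at the last occasion on which the subject was assessed for AEs.

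The end of AE collection is stated in several ways:
- Synopsis, Safety Evaluations: "until 14 days after the last administration of study drug".
- Synopsis, Study Design: "All subjects will be followed up for approximately 14 days after the last dose of study drug".
- Section 8.2.1: to the EOS Visit.
- Section 8.2.1.2: "until the end of their participation in the study, i.e., the subject has discontinued or completed the study".
- Section 4.5 asks for a full data collection when a dosed subject withdraws early, and then says: "If deemed necessary by the Principal Investigator, the subject will be asked to return at the regularly scheduled EOS Visit".

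Section 3.2 lists TEAE incidence as a secondary endpoint.

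**The concern.** A TEAE must first be an AE. If the definition keeps an event off the form, the 9.7.1 tables cannot recover it, however wide the TEAE window is. The population makes this more than a drafting point. Section 5.2 admits metformin-treated type 2 diabetes, HbA1c up to just under 9.0% and systolic pressure up to just under 160 mmHg, so many subjects may bring an illness that can worsen. Nor is early Follow-up necessarily drug-free: section 2.4.1.1 reports quantifiable drug at 72 hours in 3 of 6 subjects after a single 240 mg dose.

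For subjects who leave early, 9.7.1 ties the window to the last AE assessment, and 4.5 leaves that assessment to the investigator's judgement. Two subjects with the same exposure could have different TEAE windows.

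The study has no control arm in which the same loss would occur and partly cancel. Any error runs towards fewer reported events.

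**Working it through.** The plan gives no TEAE rate, dropout rate or power figure on this point, so there is nothing of its own to reproduce. The check is mainly a comparison of texts.

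**Step 1. Follow each kind of event through the rules.**

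| Event | AE under 8.2.1.1.1? | Inside the collection window? | Outcome in 9.7.1 |
|---|---|---|---|
| New onset in Follow-up, completer | Yes | Yes (synopsis, 8.2.1; AE monitoring at the Follow Up/EOS visit in Table 1) | Counted |
| Pre-existing illness worsens in Follow-up | No, unless recorded as a clinically significant laboratory abnormality under 8.2.2 | Yes | Timing is met, but the event is not an AE, so it is lost |
| New onset within 14 days of last dose, after early exit | Yes | Yes by the synopsis and 8.2.1; no by 8.2.1.2 | Counted only if the subject is assessed again, which 4.5 leaves open |
| Pre-existing illness worsens in screening or run-in only | No | Yes | Before first dose, so not a TEAE either way |

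Rows 2 and 3 are the defect.

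**Step 2. Length of the affected window.** Inputs: 28 treatment days (4.3) and Follow-up of up to 14 days (4.1, 4.3).
- Completer: 14/(28 + 14) = 33% of days after first dose, at most. This is a share of days, not of events.
- Early leaver with last dose on day d and no return visit: 14/(d + 14) of the window that ends 14 days after last dose. Day 7 gives 14/21 = 67%, day 14 gives 14/28 = 50%, and day 21 gives 14/35 = 40%.

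**Step 3. Effect of one missed subject.** 100/30 = 3.3 percentage points at the planned enrolment (4.1), or 100/25 = 4.0 points at the number in 9.9.

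**Step 4. Illustration for early leavers, on assumptions that are not in the documents.** Let p be the 42-day TEAE incidence (30% to 70%) and s the share who leave at day 14 without returning (10% to 30%). Assume a constant hazard, and leaving unrelated to having had an event. The loss in measured incidence is s × [(1 − p)^(14/42) − (1 − p)^(28/42)].
- p = 0.3, s = 0.1: 0.1 × (0.888 − 0.788) = 1.0 point.
- p = 0.5, s = 0.2: 0.2 × (0.794 − 0.630) = 3.3 points.
- p = 0.7, s = 0.3: 0.3 × (0.669 − 0.448) = 6.6 points.

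**Step 5. What the documents offer on discontinuation.** In the multiple-dose part of the earlier study, 1 of 13 subjects on ARD-101 discontinued (2.4.3): 7.7%, exact 95% CI 0.2% to 36%. Applied to 30 subjects this is 2.3 (0.06 to 10.8). Those were healthy volunteers dosed for 14 days, so the figure only illustrates how few subjects may be involved.

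**The case against.** The strongest reply is that most off-drug events are captured, and this stands. A reader might infer that the rules shut out off-drug events altogether. They do not: 8.2.1.1.1 expressly records events in post-treatment follow-up, Table 1 schedules AE monitoring at EOS, and 8.2.2 makes a clinically significant laboratory abnormality at EOS an AE. Serious events are recorded to EOS, and later if judged related (8.2.1.4). The remaining gap is worsening of a pre-existing illness that does not show in the laboratory. For that gap the general sentence on follow-up does not help, because the next paragraph is a specific exclusion. Even on a kinder reading, two adjacent paragraphs give site staff different answers.

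A reader might also infer that early leavers have no required AE collection after their last dose. That holds only if 8.2.1.2 and 4.5 override the synopsis and 8.2.1, and nothing says that they do. Section 4.5 requires full data at withdrawal, and 8.2.1.5 follows open AEs to an outcome, though it does not look for new ones. It can also be argued that stopping drug is not leaving the study, since 6.5, 6.6 and 6.9.2 speak only of stopping treatment. But 7.1 lists an adverse event as a reason for ending participation, 9.3 lists discontinuations by date of study exit, and no section describes a subject who stops drug and stays on study. The contradiction stands; a settled cut-off does not.

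Finally, a subject who stopped because of a TEAE is already in the overall numerator, so losing later days cannot lower overall incidence through that subject. This also stands, and it narrows the exposure.

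**Conclusion.** The concern holds as two conflicts with the protocol's own AE window. First, worsening of a pre-existing illness in Follow-up fails the AE definition in 8.2.1.1.1, although it falls within 8.2.1 and meets the timing in 9.7.1; laboratory-detected worsening is the exception. Second, for subjects who leave early, the end of AE collection is contradictory, and in practice the TEAE window depends on a discretionary visit.

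The direction is clear: TEAEs may be under-counted. The exposure lies mainly in worsened comorbidity, in the SOC/PT and severity tables, and in overall incidence among subjects who left for reasons other than a TEAE.

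The size cannot be derived from the documents. The 1.0 to 6.6 points above rest wholly on the stated assumptions, including that leaving is unrelated to events. The early-leaver loss is zero if sites follow the synopsis and 8.2.1, and the first loss is zero if no pre-existing illness worsens in Follow-up. A firm statement that incidence is under-counted, or by how much, is not supported. Even so, a rule that can remove events from a secondary endpoint, at 3.3 points per missed subject, should be corrected when the correction is this cheap.

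**What to change.** - In 8.2.1.1.1, replace the limit to the Treatment Period with *at any time from signing of the ICF to the EOS Visit*. This matches 8.2.1 and lets the 9.7.1 definition work.
- Reconcile 8.2.1.2 and 4.5 with the synopsis and 8.2.1, so that AE collection runs to 14 days after each dosed subject's own last dose. This should include subjects who stop early and have not withdrawn consent, and should use the existing Follow-up visit. In 4.5, remove the investigator's discretion over that visit and time it from the subject's own last dose.
- State the same end point in 9.7.1, so that the TEAE window does not vary with who was recalled.

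The cost is a few wording changes, a visit already in Table 1 becoming routine for a small number of early leavers, and possibly a slightly higher reported TEAE count.

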8.2.1.1.2. Definition of Serious Adverse Event

An SAE is defined as any untoward medical occurrence that at any dose:

- Results in death
- Is life-threatening; this means that the subject was at risk of death at the time of the event; it does not mean that the event hypothetically might have caused death if it were more severe
- Requires inpatient hospitalization or prolongation in existing hospitalization
- Results in persistent or significant disability/incapacity or substantial disruption of the ability to conduct normal life functions
- Is a congenital anomaly/birth defect, or
- Is another important medical event (see below)

Important medical events that do not result in death, are not life-threatening or do not require hospitalization may be considered SAEs when, based on appropriate medical judgment, they may jeopardize the subject and may require medical or surgical intervention to prevent one of the outcomes listed above. Examples of such medical events include allergic bronchospasm requiring intensive treatment in an emergency room or in a physician's office, blood dyscrasias or seizures that do not result in in-patient hospitalization, and the development of drug dependency or drug abuse.

A distinction should be drawn between serious and severe AEs. Severity is a measure of intensity whereas seriousness is defined by the criteria above. For example, a mild degree of gastrointestinal bleeding requiring an overnight hospitalization for monitoring purposes would be considered an SAE but is not necessarily severe. Similarly, an AE that is severe in intensity is not necessarily an SAE. For example, alopecia may be assessed as severe in intensity but would not be considered an SAE.

Medical and scientific judgment should be exercised in deciding if an AE is serious and if expedited reporting is appropriate.

8.2.1.2. Recording of Adverse Events

Adverse events should be collected and recorded for each subject from the date the ICF is signed until the end of their participation in the study, i.e., the subject has discontinued or completed the study.

Adverse events may be volunteered spontaneously by the subject, or discovered by study staff during physical examinations or by asking an open, non-leading question such as ‘How have you been feeling since you were last asked?’ All AEs and any required remedial action will be recorded. The nature of AE, date (and time, if known) of AE onset, date (and time, if known) of AE outcome to date, severity and action taken of the AE will be documented together with the Principal Investigator’s assessment of the seriousness of the AE and causal relationship to study drug and/or study procedure.

All AEs should be recorded individually in the subject’s own words (verbatim) unless, in the opinion of the Principal Investigator, the AEs constitute components of a recognized condition, disease or syndrome. In the latter case, the condition, disease or syndrome should be named rather than each individual symptom. The AEs will subsequently be coded using the Medical Dictionary for Regulatory Activities (MedDRA). Severity of AEs will be graded using the Toxicity Grading Scale for Healthy Adult and Adolescent Volunteers Enrolled in Preventive Vaccine Clinical Trials (September, 2007).

